Iceland are eligible participants (n=661, m:f ratio=313:348). All children in public schools in the municipality are equipped with an iPad from 10 years of age. Exclusion criteria are diagnosis of severe disorder of intellectual development and/or physical-, developmental- and mental illness significantly restricting ability to use mobile apps. Research specifications and introduction to the application will be sent via email to parents and legal caretakers of all eligible participants through school officials along with confirmative survey link. If the link is answered, it yields confirmation for informed consent. Adolescents with informed consent from parents/legal caretakers will then invited to take part in the study through confirmative survey link. The study has been approved by the National Bioethics Committee (license number: VSNb2015060065/03-01).

Measurements

Original primary outcome measure will be app acceptability and functionality, measured with *Systematic Usability Scale* (SUS), a widely used and relatively well studied 10-item questionnaire on app usability where scores range from 0-100 and total score over 70 yielding satisfactory usability and user acceptance [40, 41]. Further primary measures were amount, frequency and time of daily physical activity measured through in-app activity, self-reported stress levels, quality of sleep and energy levels, measured through levels of the health app usage and completion of in-app health tasks.

Secondary outcome measures include standardized body mass index (*BMI-SDS*) based on BMI index reference values for Swedish children and adjusted for age and sex. Participants are weighed in kilograms in light clothing without shoes using a digital scale (Marel type C2; Marel, Reykjavik, Iceland). Height is measured in centimetres using a wall-mounted stadiometer (Seca stadiometer; Seca, Hamburg, Germany).

Anxiety and depressive symptoms will be assessed using the *Revised Children's Anxiety and Depression Scale* (RCADS), a self-report assessment tool for children and youth. The scale is a four point Likert scale, spans 47 questions and is divided into 6 subscales; separation anxiety symptoms, general anxiety symptoms, obsessive-compulsion symptoms, social anxiety symptoms, panic symptoms, depression symptoms. A *T*-score over 65 marks a clinical cut-off point. The inventory's psychometrics have been studied with acceptable findings in both US and Icelandic paediatric populations [42, 43].

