SidekickHealth was initially developed through multiple focus group studies amongst both Icelandic elementary school students and adolescents in the obesity clinic at the Landspítali University Hospital in Iceland to incorporate the target groups' needs and opinions. Based on results from focus-group studies and design advisors, the app took the form of a social health game (see Figure 1). Functionality of the app evolves around motivational support to help the user set goals and complete health tasks (gamification of tasks), in three main categories: food and drink (e.g. vegetable and water intake, consumption of fruits, avoiding sugary soda or energy drinks), physical activity (e.g. body-weight exercises, logged minutes of sports activity, gps-based biking, walking or running), and mental health exercises (e.g. reducing stress, exercising gratitude and improving sleep habits). By completing health tasks that are labelled missions and participating in friendly competitions with peers, users earn points (called "kicks") and badges providing altruistic rewards (e.g. litres of water for children in need or polio vaccinations that are sent in their name to children in need through UNICEF). A visual representation of the user's performance is provided in different categories. Keeping the app fun, entertaining, and easy-to-use is of integral importance and was a strong focus point throughout all developmental phases. The smartphone application operates on Android and iOS platforms. The app's function focuses on education and simple health behaviour changes through the benefits of increased physical activity and mental health exercises as well as a healthy diet, portion sizes, and appetite awareness training (AAT). AAT is a behaviour modification tool that has for instance been used in obesity treatment and encourages overweight/obese children and youth to consume food and drink in response to internal appetite cues. It has shown promise for the treatment of overweight and obese children and teenagers and has been visually developed as an individual mission in the app's nutrition category [48, 49]. Participants in the intervention realm will be randomly assigned to groups consisting of 8 individuals which collectively and individually competed in point collection through completion of in-app health tasks. In the beginning of each of the trial's 6 weeks, the intervention group receives in-app messages where a new weekly competition (both individual and on group level) with altruistic rewards is introduced. In weeks 2 to 6, altruistic rewards for past week's efforts will also be handed out. Winners of competitions receive confirmation that UNICEF had sent Polio vaccinations to children in need. Further, through completion of in-app health exercises participants collect litres of water that will be sent in their name to children in need through UNICEF. The total cost for the altruistic rewards for all in-app rewards throughout the treatment period was roughly estimated to be between 50 to 100 US dollars or roughly 50 US cents per participant.

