
Figure 1. Overview of app functions & categories

[figure not shown]

Procedure

The study is a randomized controlled study. Cluster randomization is used to distinguish three participating schools into control, treatment-as-usual (TAU) and intervention groups. Measures will be obtained at baseline and 42 days later. Participants in both the TAU group and the intervention group receive an approximately 10 minutes long introduction regarding the study specifications and the application. The control group receives no further contact, access to the application or information until study-end questionnaire measures. Participants in the intervention group are randomly assigned to teams consisting of 8 individuals that collectively and individually compete in point collection through completion of in-app health tasks. Participation in the TAU group and intervention group is defined as downloading the Sidekick app and completing at least 3 health exercises within it. Time of exercise is defined as the timestamp on completion of exercise within any of the three types of exercise categories (physical activity, nutrition and mental health) of the app. Exercise frequency refers to how often a given exercise was completed by a participant. Time of attrition was defined as the time stamp of last completing health exercise within the Sidekick throughout intervention period. The procedural difference between TAU group and intervention group evolves around motivational support. The intervention group receives weekly motivational support in form of individual and group feedback on usage, participation in friendly health task competitions and weekly altruistic rewards for usage. Participants in TAU group use the

application individually throughout trial period without any motivational support. A flow chart of participation is displayed in figure 2.

Figure 2. Participant flow chart

Statistical analysis

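### A TAU versus intervention difference in the app-recorded physical activity outcome may partly reflect more, or invented, logging, because contests on completed tasks are described for the intervention arm only

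*Combined protocol and SAP*

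**What the plan says.** **Outcome.** The combined protocol and SAP, under Measurements, states: "Further primary measures were amount, frequency and time of daily physical activity measured through in-app activity". The same sentence goes on to other self-reported measures and ends with the means of measurement: "measured through levels of the health app usage and completion of in-app health tasks". The secondary measures listed there are BMI-SDS and questionnaires on anxiety and depression, self-efficacy and sleep. None of them records physical activity.

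**What feeds the outcome.** Under mHealth application, the app's activity category is given as "physical activity (e.g. body-weight exercises, logged minutes of sports activity, gps-based biking, walking or running". Procedure then defines the recorded units: "Time of exercise is defined as the timestamp on completion of exercise within any of the three types of exercise categories", and "Exercise frequency refers to how often a given exercise was completed by a participant". Neither definition refers to how an entry was made.

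**What differs between the arms.** Under Procedure, intervention pupils are placed in teams of eight that "collectively and individually compete in point collection through completion of in-app health tasks". Their weekly support includes "participation in friendly health task competitions and weekly altruistic rewards for usage". TAU pupils use the same app on their own, without motivational support. The control school has no access to the app.

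**Analysis.** Statistical analysis lists t-tests, repeated measures ANOVAs and chi-square tests for differences within and between groups on the primary and secondary outcomes. It mentions no split by source of record and no check on entries.

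**The concern.** The TAU versus intervention contrast is meant to show what motivational support does. For this outcome, the support also rewards the act of making a record. If part of the record can be made without the activity, or if real activity is more likely to be recorded when points are at stake, the measurement error differs by arm and favours the intervention.

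This is not only a matter of how long pupils keep using the app. It can operate on each active day and among pupils who stay to day 42, so allowing for attrition or time in use would not remove it. A larger sample would not help either: it makes a false difference of a given size more likely to reach significance.

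At stake is the second stated aim, which is whether the intervention increases daily health behaviour, physical activity included. The control arm has no app data, so TAU is the only comparator for this outcome.

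**Working it through.** **Step 1: the text.** There is no figure in the plan to reproduce, because the documents give no target sample size, effect size, standard deviation or power. The point rests first on the text:

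| Element | Where | What it establishes |
|---|---|---|
| Activity is measured from in-app records | Measurements | No outside check on the value |
| One category holds logged minutes, body-weight exercises and GPS tasks | mHealth application | Mixed sources, some apparently self-logged |
| Units are completion time and number of completions | Procedure | No split by source |
| Contests turn on completed tasks | mHealth application, Procedure | Recording carries a reward in the intervention arm |
| TAU has no motivational support | Procedure | No contest described there |
| Primary outcomes are compared between groups | Statistical analysis | No analysis by source |

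The Cox model includes exercise type, but the types the plan defines are the three health categories, and that model predicts attrition and not activity. It does not deal with the issue.

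**Step 2: an illustration of size.** None of the following inputs is in the documents; all are assumptions.

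- True activity is equal in TAU and intervention.
- Self-logged share of recorded activity, h: 0.5 to 0.8.
- Over-entry of that share in the intervention arm only, o: 0.10 to 0.30.
- Coefficient of variation of recorded activity, CV: 0.6 to 1.0.
- n = 100 pupils per arm. This is compatible with the stated reward budget: 50 to 100 US dollars at roughly 50 cents per participant gives 50/0.5 = 100 to 100/0.5 = 200 pupils.
- Two-sided alpha of 0.05 (the plan gives p < .05 without sidedness).

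Formulas: false relative excess = h × o; standardised difference d = h × o / CV; noncentrality = d × √(n/2). The probability of p < .05 is then the power of a two-sample t-test at d.

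| Case | h | o | CV | False excess | d | d × √50 | P(p < .05) |
|---|---|---|---|---|---|---|---|
| Lowest | 0.50 | 0.10 | 1.0 | 5% | 0.050 | 0.354 | 6.4% |
| Midpoint | 0.65 | 0.20 | 0.8 | 13% | 0.1625 | 1.149 | 21% |
| High share, high CV | 0.80 | 0.20 | 1.0 | 16% | 0.160 | 1.131 | 20% |
| High share, low CV | 0.80 | 0.20 | 0.6 | 16% | 0.267 | 1.886 | 47% |
| Highest | 0.80 | 0.30 | 0.6 | 24% | 0.400 | 2.828 | 80% |

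**Step 3: sensitivity to n.** Take h = 0.5, o = 0.25 and CV = 1.0, a false excess of 12.5%. The false-positive rate is about 9.5% with 50 per arm, 14% with 100, and 26% with 220 (about 661/3, full uptake in schools of equal size).

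Each arm is one school. The calculation ignores that, so it isolates the logging effect and is not the trial's overall error rate.

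**The case against.** The strongest reply is that much of the mechanism is inferred.

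- **Entry mode.** The plan speaks of logged minutes; it does not say that pupils type them in, and it does not say how body-weight exercises are recorded. The list is introduced as examples, and the figure that gives an overview of app functions is not in the text available for review. This stands, so the self-logged share is unknown.
- **Incentive.** Points are tied to completing tasks. Nothing says they rise with minutes entered, so a motive to round minutes up is not documented; a motive to record more completions is. Nutrition, mental health and GPS tasks can count as well, and the rewards are altruistic and small. This stands too.
- **TAU features.** Points, badges and altruistic rewards are described as general features of the app, and which of them TAU pupils see is not spelled out. The weekly contests, however, are described only for the intervention group.
- **Analysis.** The tests are listed generically, and the activity variable might be analysed exercise by exercise. That is possible, but no such analysis is specified.
- **GPS data as the answer.** Contest pupils also have more reason to switch GPS recording on, and a GPS-only outcome would drop sport and body-weight exercise, which the app promotes. This is a good argument against replacing the primary outcome.

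A reader might infer that hand entries are what wins the contests, that over-logging takes place, or that the comparison is biased by a known amount. The documents support none of these. They show that the outcome is open to this error in one direction, and that nothing planned would reveal it.

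**Conclusion.** The point holds as a weakness in how the outcome is defined and interpreted. The primary activity measure comes only from app records of mixed type, the described contests reward recording in the intervention arm only, and no analysis separates the sources. A TAU versus intervention difference therefore cannot, as planned, be read as a difference in physical activity alone.

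The size is undetermined. The range of about 6% to 80% at 100 per arm, with about 21% at the midpoint, depends wholly on assumed shares, over-entry and spread, and ignores school clustering. The upper figures pair the highest self-logged share with the smallest spread and should not be quoted as expected values. At the lower end the effect is close to the nominal 5%. The change is worth making because it is cheap and protects the second aim, not because bias has been demonstrated.

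**What to change.** In the SAP:

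1. Describe the outcome as app-recorded task completion, and not as physical activity without qualification.
2. State how each type of activity task is recorded, and which point, badge and reward features TAU pupils see.
3. Split the outcome into GPS-based and self-logged tasks, and show each type's share by arm.
4. Pre-specify the TAU versus intervention comparison of GPS-based tasks as a sensitivity analysis, not as a replacement primary outcome.
5. State in advance that a difference seen only in self-logged tasks will not be taken to show that motivational support increased physical activity.
6. Name differential recording of real activity as a limitation. It remains in both sources.

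The cost is SAP wording, a task-type field in the log extract (if the log holds it, which the documents do not say) and a little more analysis. The GPS subset covers fewer activities and pupils, so its estimate will be less precise.

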Increased knowledge on actual attrition factors and patterns in adolescent populations from mHealth interventions are direly needed. Obtaining a better understanding of how motivational support motivates adolescents to use mHealth applications and why they maintain or lose interest in using them to improve their health is of vital importance. Motivational support in mHealth interventions, defined as strategies to enhance motivation and counter attrition to overcome behavior change barriers, often include goal-setting, feedback, social support and rewards (36-37). Systematic reviews examining possible drivers behind usage point to group and task customization, localization, functional user support, gamification of health tasks and immediate visual but simplified feedback on user action while while gender-related motivational support features could be contributing factors [36-38]. Timing of tailored motivational support, through just-in-time adaptive interventions (JITAI), should be considered as well when implementing adolescent mHealth interventions since time-based individualization could counter high attritions rates [35, 39]. Given the magnitude of reported health problems among adolescents and lack of cost-effective health behaviour interventions specifically developed for adolescent populations, the need for better understanding of attrition reasons in adolescent mHealth interventions is massive. The purpose of this study was firstly to seek richer understanding of continuous attrition rates from a mHealth intervention in an adolescent population and what effects motivational support has on attrition rates. Secondly, the aim was to examine effectiveness of the intervention with the aim to increase daily mental, nutritional and physical health behaviour.

Methods

Participants

Participants are adolescents, age 13 to 16 years old, attending one of three public schools for children and adolescents in the greater capital area of Iceland. All children attending the oldest 3 classes, called 8th to 10th classes, in three participating public elementary schools in

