General Self Efficacy Scale (GSE), a 10 item self-report questionnaire with ranging total scores from 10 to 40, is used to measure self-efficacy levels where higher score yielding increases self-efficacy [44]. Acceptable psychometric properties for the questionnaire have been obtained and it is used globally in youth populations [45].

[figure not shown]
BEARS sleep screening algorithm will be used to evaluate participant's sleep problems. It is a sleep screening instrument for children from 2 to 18 years old, divided into 5 sleep domains; bedtime problems, excessive daytime sleepiness, awakenings during night, regularity and

duration of sleep and snoring [46]. The algorithm's psychometrics have been studied with acceptable findings in paediatric populations [47].

mHealth application

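### As written, the primary outcomes for stress, sleep quality and energy are scored from app use, which is exposure to the intervention and is encouraged more in one arm

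*Combined protocol and SAP*

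**What the plan says.** The Measurements section names the SUS as the original primary outcome and then adds others. The addition opens with "Further primary measures were amount, frequency and time of daily physical activity measured through in-app activity" and continues with "self-reported stress levels, quality of sleep and energy levels, measured through levels of the health app usage and completion of in-app health tasks". For stress, sleep quality and energy it gives no item, scale, score, direction or time point.

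Other measures in the same section do not depend on app use: BMI-SDS, RCADS, GSE and BEARS ("BEARS sleep screening algorithm will be used to evaluate participant's sleep problems"). All of them come after the sentence that introduces the secondary outcomes.

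The Procedure section says that the two app arms differ in motivational support. The intervention arm receives weekly individual and group feedback, "participation in friendly health task competitions and weekly altruistic rewards for usage". TAU pupils use the "application individually throughout trial period without any motivational support". The control arm has no app and is not contacted again until the closing questionnaires. Measures are taken at baseline and at 42 days. The exercise log also dates attrition: "Time of attrition was defined as the time stamp of last completing health exercise within the Sidekick throughout intervention period".

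The Statistical analysis section plans baseline-to-end comparisons, within and between groups, on primary and secondary outcomes alike. It starts the trial clock at the first completed in-app exercise.

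**The concern.** Completing a stress or sleep mission shows that the pupil did or logged the mission. It does not show that stress fell or that sleep improved. In this trial the scored quantity is also what the randomised contrast is designed to raise, because motivational support exists to keep pupils using the app. A difference between TAU and intervention on these outcomes could therefore be reported as lower stress, better sleep or more energy when pupils had only logged more tasks or used the app for longer. These are primary outcomes, and no analysis of the log can recover a construct that was not measured.

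**Working it through.** The plan states no sample size, power, effect size or SD, so there is no design figure to reproduce. The one count that can be checked agrees: 313 + 348 = 661 eligible pupils, or 661 / 3 = about 220 per school if the schools are of equal size. The rest is a comparison of sections, followed by an illustration.

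**1. What is scored.** Taken literally, the Measurements sentence makes app use and completed tasks the measuring tool for all three constructs. No other source is named for them.

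**2. What differs between the app arms.** The last background paragraph before Methods says that strategies of motivational support "often include goal-setting, feedback, social support and rewards". The Procedure section gives weekly feedback, competitions and weekly rewards to the intervention arm and withholds motivational support from TAU. The contrast therefore acts directly on the scored quantity.

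**3. Whether the planned comparison exists.** It needs a baseline and an end value in each group.
- Control: no app, so neither value exists.
- TAU and intervention: pupils have no app use before they receive the app, and the clock starts at the first exercise, so there is no pre-intervention value.

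Only a post-start comparison of TAU with intervention remains.

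**4. The other reading.** Suppose the words on self-report mean ratings entered in the app. A rating does address its construct. But it would exist only on days of use and would end at attrition, the event that motivational support is meant to delay. The arms would be compared over different, selected pupil-days, and the control arm would still have no data.

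**5. Illustration, all inputs assumed.** Let the true effect on health be zero and let use differ by d SD between the two app arms, with n pupils per arm. The probability of a significant result at two-sided 0.05 (sidedness is not stated in the plan) is

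Φ(d/√(2/n) − 1.96) + Φ(−d/√(2/n) − 1.96).

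For d = 0.3 and n = 100: 0.3/√0.02 = 2.12, Φ(0.16) = 0.56, and the second term is negligible.

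| n per arm | d = 0 | d = 0.1 | d = 0.2 | d = 0.3 | d = 0.5 |
|---|---|---|---|---|---|
| 50 | 0.05 | 0.08 | 0.17 | 0.32 | 0.71 |
| 100 | 0.05 | 0.11 | 0.29 | 0.56 | 0.94 |
| 220 | 0.05 | 0.18 | 0.56 | 0.88 | 1.00 |

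Clustering by school is ignored. More pupils make the false conclusion more likely.

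On the raw scale, also assumed: if behaviour is identical but 30% of eligible tasks are logged in TAU and 50% in the intervention arm, the recorded count is 0.50/0.30 = 1.67 times as high (+67%). If mean use is 14 of the 42 days against 28 at the same daily logging rate, the mean total is 28/14 = 2 times as high. The plan does not define the outcome as a 42-day total, so these two figures show only how the problem arises.

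**The case against.** The sentence in question ends a long, loosely punctuated list and does call the outcomes self-reported. Its last clause may mean only that the app is where the data come from. This stands as an ambiguity. On that reading the fault is selectively missing data, not a wrong construct.

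A reader might infer four stronger conclusions that the documents do not support.

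- *Use is rewarded only in the intervention arm.* The mHealth application section describes points and "badges providing altruistic rewards" for users in general, and nothing says that these are switched off in TAU. Only the weekly feedback, competitions and weekly rewards are clearly confined to the intervention arm. The incentive differs between the arms but may not be absent in TAU.
- *The bias must favour the intervention arm.* On the literal reading, more logging does push that way if a higher count is taken as better health. With in-app ratings the direction is unknown: support that keeps less motivated pupils in the app for longer could work against that arm.
- *These outcomes merely repeat the attrition endpoint.* Attrition is the time of the last exercise. The log also holds amount, type and frequency, which the Cox models use as predictors of attrition. The measures overlap but are not the same.
- *The effectiveness aim has no valid measure.* RCADS, GSE, BEARS and BMI-SDS do not depend on app use. The second aim is also worded as health behaviour, and completing a mental-health task is arguably such a behaviour. That supports reporting completions as logged behaviour. It does not make them a measure of stress, sleep quality or energy.

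**Conclusion.** The point holds for these three primary outcomes, not for the trial as a whole. Followed as written, the plan scores app use as stress, sleep quality and energy, and a difference between TAU and intervention cannot be separated from differential encouragement to use the app. That the control arm cannot supply the measure, and that no pre-intervention value exists, follows from the Procedure and Statistical analysis sections under either reading.

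The size cannot be derived from the documents. Over assumed differences in use of 0.2 to 0.5 SD and 50 to 220 pupils per arm, the chance of a significant result with no health effect runs from 0.17 to nearly 1, against a nominal 0.05. This assumes the literal reading, a two-sided test and no clustering. If in-app ratings were intended, these figures do not apply, and the problem is missing data of unknown direction.

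**What to change.** 1. State what measures stress, sleep quality and energy: the item or scale, its score and direction, and when and in which arms it is given.
2. Report app-use and task-completion counts as engagement or logged behaviour under the attrition aim, and do not interpret them as stress, sleep quality or energy. State whether points, badges and water rewards are active in TAU.
3. Rest the sleep claim on BEARS and the emotional-health claim on RCADS, both at baseline and day 42 in all three arms. Both are already planned. Declare and date any change between primary and secondary status, and say whether it was made before the data were seen.
4. Neither instrument is a dedicated stress or energy scale. If baseline has not been collected, add one self-rating item for each at baseline and day 42 in all arms. If it has, drop stress and energy from the effectiveness claim. The text mixes future and past tense, so the sponsor must say which case applies.

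The cost is protocol and SAP wording plus at most two questionnaire items. The downside is that the sleep and emotional-health claims, and any stress and energy claims, would rest on two time points instead of daily data.
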